Ethnic Differences in Antihypertensive Medication Response among Pregnant and Postpartum Patients

[name]

NCT03506724

11/2017

Protocol

Patients were randomized to first receive IV labetalol or oral nifedipine and the number of doses of each medication that was given was recorded. The protocol used for medication administration was the same as the ACOG protocol for treatment of acute hypertension in pregnancy (See medication specific protocol below). Blood pressure for all women in the study was taken in the right arm with an automated blood pressure cuff while the patient was resting in bed in the semi-recumbent position. The systolic blood pressure and diastolic blood pressure was recorded before and after administration of each medication. A short survey to assess patient-reported side effects were provided prior to and post medication administration.

IV Labetalol protocol

Labetalol 20mg IV was given over 2 minutes and the systolic and diastolic blood pressures were recorded 10 minutes after the medication was given. If SBP was ≥ 160 mmHg or DBP was ≥ 110 mmHg, labetalol 40mg IV was given over 2 minutes and the systolic and diastolic blood pressures were recorded 10 minutes after the medication was given. If SBP was ≥ 160 mmHg or DBP was ≥ 110 mmHg, labetalol 80mg IV was given over 2 minutes and the systolic and diastolic blood pressures were recorded 10 minutes after the medication was given. If SBP was ≥ 160 mmHg or DBP was ≥ 110 mmHg, then another medication was chosen based on institution specific protocol. (ACOG Safe Motherhood Initiative)

Oral nifedipine protocol

Nifedipine 10mg oral was given and the systolic and diastolic blood pressures were recorded 20 minutes after the medication was given. If SBP was ≥ 160 mmHg or DBP was ≥ 110 mmHg,

nifedipine 20mg oral was given and the systolic and diastolic blood pressures were recorded 20 minutes after medication was given. If SBP is ≥ 160 mmHg or DBP is ≥ 110 mmHg, nifedipine 20mg oral was given and the systolic and diastolic blood pressures were recorded 20 minutes after medication was given. If SBP was ≥ 160 mmHg or DBP was ≥ 110 mmHg, then another medication was chosen based on institution specific protocol. (ACOG Safe Motherhood Initiative)

Statistical Analysis

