In the following sample size calculation, our primary aim is to detect an interaction effect between race and hypertensive treatment on time to reach goal blood pressure. We assume that the race distribution would be 20% for African Americans and 80% for Caucasians or Asians entering the clinic during the trial enrollment period. Randomization will be stratified by race at a 1:1 ratio to Nifedipine or Labetalol.

We assume the minimally clinical difference for African American patients on Labetalol is expected to take 30 minutes longer compared to patients on Nifedipine to reach their goal blood pressure. For Caucasian or Asian patients, those on Labetalol are expected to take 20 minutes longer compared to those on Nifedipine to reach their goal blood pressure. We expect residuals to be normally distributed with a mean of 0 and standard error of 8. We assume that time to goal blood pressure is normally distributed and power to detect an interaction by a linear regression is at least 85% with an alpha of 0.05.

Based on the above, we used a simulation approach to estimate that we would need a total of 146 patients to provide at least 85% power to detect an interaction effect between race and hypertensive treatment.

Power	Assumed Effect Size for African Americans	Assumed Effect Size for Caucasians or Asians	Assume Proportion of African Americans	Minimal Number of African Americans	Minimal Number of Caucasians or Asians	Total N
0.85	30 min	20 min	40%	40	58	98
0.90	30 min	20 min	40%	46	68	114

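### Linear regression on time to goal has no stated value for women still at or above 160/110 after the third dose; if the clock stops there, dropping or capping them biases the race-by-drug interaction

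*Combined protocol and SAP*

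**What the plan says.** The Statistical Analysis section sets the objective: "our primary aim is to detect an interaction effect between race and hypertensive treatment on time to reach goal blood pressure". It treats the outcome as complete and Gaussian: "We assume that time to goal blood pressure is normally distributed". The single model mentioned appears in the power statement: "power to detect an interaction by a linear regression is at least 85% with an alpha of 0.05". The assumed effects are "African American patients on Labetalol is expected to take 30 minutes longer compared to patients on Nifedipine" and, for Caucasian or Asian women, "those on Labetalol are expected to take 20 minutes longer compared to those on Nifedipine". The target interaction is therefore 30 − 20 = 10 min. The spread is given as "We expect residuals to be normally distributed with a mean of 0 and standard error of 8".

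The Protocol section opens with "Patients were randomized to first receive IV labetalol or oral nifedipine". Each drug then has up to three timed doses. A woman whose systolic pressure is at least 160 or diastolic at least 110 at the third reading leaves the scheme: "then another medication was chosen based on institution specific protocol".

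Several things are not stated:
- the goal as a number;
- whether time keeps running after the change of drug;
- any reading scheduled after that change;
- what value a woman not at goal receives;
- any censored or time-to-event method.

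**The concern.** An ordinary linear regression needs one completed time per woman. The protocol foresees women for whom, on the randomised drug, all that is known is that the time exceeds the last reading. Unless the clock runs on and a later time is recorded, the analyst must leave such a woman out or enter her last reading as if goal had been reached then. Under the plan's own effects these women are mostly on labetalol and most often African American. That is the cell that carries the interaction, so the loss bears directly on the primary estimate and its power.

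**Working it through.** **Inputs.** From the Statistical Analysis section: effects of 30 and 20 min; 8 min, read as the residual SD; 20% African American (AA); 1:1 allocation within race; N = 146; alpha 0.05, taken as two-sided. From the two drug protocols: the step lengths and the 160/110 threshold. Assumptions not in the documents: goal means below 160/110; mean nifedipine time is the same in both races and varied; the clock stops at the third reading.

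**1. The plan's figure.** Group sizes are 0.2 × 146 = 29.2 and 0.8 × 146 = 116.8. The standard error of the interaction is 8 × √(4/29.2 + 4/116.8) = 3.31 min, and 10/3.31 = 3.02. The noncentral t with 142 df gives power 0.851. So 146 is reproduced, for fully observed times.

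**2. Where the steps end.** Labetalol: 3 × (2 + 10) = 36 min (30 min if the 10 minutes run from the start of the injection). Nifedipine: 3 × 20 = 60 min.

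**3. Effect on the planned interaction.** For a cell with mean m and limit c, let k = (c − m)/8.
- Capped mean = mΦ(k) − 8φ(k) + c(1 − Φ(k)).
- Mean after dropping = m − 8φ(k)/Φ(k).

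Take a nifedipine mean of 8. AA labetalol has m = 38 and k = −0.25, so the capped mean is 33.71 and the dropped mean 30.29. Other labetalol has m = 28 and k = 1, giving 27.33 and 25.70. The nifedipine cells are equal and cancel. The interaction is 33.71 − 27.33 = 6.4 min capped and 30.29 − 25.70 = 4.6 min dropped.

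The percentage not at goal is 1 − Φ(k). Power is simulated with cells of 15 and 14 (AA nifedipine, labetalol) and 59 and 58 (others).

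| Nifedipine mean (min) | Labetalol not at goal, AA / other | Dropped: min, power | Capped: min, power | Censored normal, exact times: power |
|---|---|---|---|---|
| 8 | 60% / 16% | 4.6, 16% | 6.4, 58% | 82% |
| 10 | 69% / 23% | 4.0, 9% | 5.5, 44% | 82% |
| 12 | 77% / 31% | 3.4, 4% | 4.5, 34% | 78% |

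Simulated estimates at N = 146 agree with the closed form to about 0.1 min (4.6 to 4.7, 3.9 and 3.5 dropped). Dropping costs so much power partly because at a mean of 8 only about 14 × 0.40 ≈ 6 AA labetalol women remain. At a nifedipine mean of 20 min, capping leaves 1.45 min (9% power) and dropping 1.9 min.

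**4. No true interaction.** With no race effect either, the bias is zero. If AA women are 10 min slower on both drugs and the drugs do not differ, the false interaction is −0.1 min (capped) or −0.4 min (dropped) at a nifedipine mean of 10. At a mean of 30 it is −4.5 or −5.9 min, with simulated false-positive rates of about 33% and 22%. Equal limits in both arms would give exactly zero in that setting.

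**5. Censored normal regression.** With exact times up to the limit, the estimate is about 10 min. False-positive rates were mostly 4–6%, although one 300-run set gave 8–10% in two null settings. If each time is instead recorded at the first scheduled reading at or after goal (12/24/36 or 20/40/60 min) and treated as exact, right-censoring alone recovers only about 6.6 to 7.0 min. Fitting intervals addresses this, but power was about 60% in one setting (nifedipine mean 8, 200 runs). There, Φ((20 − 8)/8) = 0.933 of nifedipine women reach goal by the first reading. All 15 AA nifedipine women do so in 0.933^15 ≈ 35% of trials, and that cell mean is then poorly determined unless the first interval is bounded at time zero. The 60% is sensitive to that choice and is only indicative.

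**The case against.** The strongest reply is that the documents never stop the clock at the third dose. Women are randomised to a first drug, and pressures and dose counts are recorded for each medication given, so time to goal may continue through the switch. The planned differences point that way: the largest difference visible within the steps is 36 − 20 = 16 min, below both 20 and 30. If the clock runs on and later times are recorded, most women have a value, the regression can be computed, and the bias above does not arise. This stands, and it makes the finding conditional. It does not remove the gap, because the continuing clock is not stated, no later reading is scheduled, and a time reached after the switch includes the effect of a second drug.

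Three stronger readings are tempting, and the documents do not support them.
- A reader might infer that the regression has no value for these women and must drop or cap them. The plan is silent; it chooses neither.
- A reader might infer that the 5% error rate is inflated in general. That needs one race to be slower on both drugs, a figure the plan does not give, and the effect is small when nifedipine times are short.
- A reader might blame the 24-min gap between the arms' limits for the loss under the planned effects. The 36-min labetalol limit causes it: setting both limits to 36 gives the same 5.5 min capped and 4.0 min dropped at a nifedipine mean of 10.

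The nifedipine means of 8 to 12 min also fit the schedule poorly. They place 84–93% of nifedipine times before the first reading at 20 min and, at a mean of 8, 16% below zero. Longer means make the loss worse.

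**Conclusion.** The concern holds in conditional form. The plan names a model that cannot represent a woman not observed at goal, foresees such women, and gives no rule for them. If time stops at the third reading, either simple handling cuts the planned interaction by roughly a third to two thirds, and power falls far below 85%. This rests on a goal of below 160/110, SD 8 with normal times, limits of 36 and 60 min, and an assumed nifedipine mean of 8 to 12 min. A spurious interaction is possible only with a race effect common to both drugs. The sample-size arithmetic is right for fully observed times; the defect lies in the outcome and analysis definitions.

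**What to change.** 1. Define goal blood pressure numerically, and state whether time to goal stops at, or runs past, the change of drug. That is the sponsor's choice of estimand. Give the other definition as a sensitivity analysis where the data allow.
2. Keep every randomised woman. Fit the same race, drug and race-by-drug terms, in minutes, as a censored normal regression. Right-censor a woman not observed at goal at her last reading under the chosen definition. Treat an observed time as lying between the last reading not at goal and the first reading at goal, and state the lower bound of the first interval.
3. Report the proportion at goal within three doses by race and drug.
4. State that the 85% applies only to fully observed times, and check power and error rate by simulation under the chosen definition.

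The cost is a few lines of text and standard software, with no new patients. With every time observed exactly, the model is the planned regression. The downsides are reliance on the normality already assumed and lower power: about 80% with exact times, and perhaps near 60% if times are known only at scheduled readings. Very high non-response would strain this model too, which is a further reason for item 3.
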